Thus, the significance of the study lies in its investigation of the combined therapeutic effects of CKC and weight-shifting exercises as a potential strategy for enhancing postural stability and overall functional outcomes in patients with unilateral post-mastectomy lymphedema. By addressing the challenges of postural instability and balance deficits, this study aims to contribute to the development of more effective rehabilitation interventions, ultimately improving the quality of life for affected individuals.

Delimitations:

This study will be delimited in the following aspects:

1. Subjects:

Sixty female patients with unilateral post mastectomy lymphedema will be randomly divided into four equal groups in number, each one has 15 patients.

2. Equipment and tools:

2.1. Measurement equipment:

2.1.a. Kinesis Balance™ fall prevention app: smartphone-based machine learning algorithm for assessing standing balance (**Greene et al., 2021**).

2.1.b. Time up and go (TUG) test: for assessing dynamic balance and gait efficiency (**Tomar et al., 2024**).

2.1.c. Functional reach test: for assessing Functional reach and dynamic balance (**Alahmari et al., 2021**).

2.2. Therapeutic equipment and tools:

2.2.a. Closed kinetic chain exercises.

2.2.b. Weight shifting exercises.

Hypothesis:

It will be hypothesized that:

Closed kinetic chain and Weight shifting exercises have no significant effect on postural stability in unilateral post mastectomy lymphedema.

Basic Assumptions:

It will be assumed that:

- All patients will continue in the study.
- All patients will follow the instructions during the treatment.
- All patients will be informed about and understood the details of the research procedure.
- All patients enrolled in the study will have their informed consent.
- The clinical methods of measurement will be reliable and valid.

Definitions of terms:

The following terms are defined for the clear understanding of the terminology that will be used in the present study:

1. Closed kinetic chain exercises (CKC):

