Sample size calculation was done using Anteroposterior stability index, as reported in (Elsayeh et al, 2018), with 95% power at $\alpha = 0.05$ level, number of measurements 2, for 4 groups and effect size = 0.6 using F-test MANOVA repeated measures within and between interaction. The minimum proper sample size is 52 subjects, adding 8 subjects (15%) as drop out, so total sample size is 60 subjects, 15 subjects in each group. The sample size was calculated using G*Power software (version 3.0.10) (figure 1).

[figure not shown]

Figure (1): sample size calculation

Sixty patients who have unilateral post mastectomy lymphedema will participate in this study. Their ages will range from 40 to 60 years. The patients will be subdivided randomly into four equal groups by using simple randomization technique 1:1 ratio to four equal groups according to sample size calculation (15 patients for each group). The allocation will be performed with a blinded investigator using sealed opaque envelopes including a code for each group to avoid allocation bias. They will be selected from the Outpatient Clinic of Faculty of Physical Therapy, Cairo University and Alexandria oncology center.

All participants were informed about nature and the effect of measurement and treatment methods and have signed the informed consent which includes their agreement to participate in the study (**Appendix I**). They were instructed to report any side effects during management.

1.1- Design of the study:

The study will be four-armed, single-blind (assessor), parallel-group, randomized control trial.

1.1.a- Group A (n= 15) (CKC group):

This group will include 15 patients who will receive closed kinetic chain exercises, in addition to complex decongestive therapy (CDT) for the treatment of lymphedema. CDT includes (skin care, manual lymphatic drainage, compression bandages, compression garments and exercises). The total exercise time will be 30 minutes, three times per week for eight weeks.

1.1.b- Group B (n= 15) (WS group):

This group will include 15 patients who will receive weight shifting exercises, in addition to complex decongestive therapy (CDT) for the treatment of lymphedema. The total exercise time will be 30 minutes, three times per week for eight weeks.

1.1.c- Group C (n= 15) (Combined group):

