Lateral weight-shifting, in particular, is essential for maintaining posture under dynamic conditions and is commonly performed in various activities of daily living (**Inoue et al., 2021**).

3-Procedures of the study:

3.1-Measurement procedures:

All patients will be evaluated before and after eight weeks of using closed kinetic chain and weight shifting exercises.

3.1.a. Kinesis Balance™ fall prevention app:

Patients will be instructed to hold the phone firmly against their sternum and stand with their eyes open, in a semi-tandem stance, for 30 s. The app contains audio and visual instructions on how to prepare for and complete the test as well as an audio cue to indicate test start and stop.

[figure not shown]

Figure (2): Shows Smartphone app for assessment of balance and falls risk using questionnaire and standing balance test (in semi-tandem stance **adapted** from (Greene et al., 2021).

3.1.b. Time Up and Go Test (TUG):

Patients will be asked to stand up from a chair with armrests, walk three meters, turn, walk back, and sit down, figure (3). The time taken to complete this task will be measured in seconds using a stopwatch (Tomar et al., 2024).

[figure not shown]

Figure (3): Shows Principle of the timed-up-and-go (TUG) test **adapted** from (Nierat et al., 2016).

3.1.c- Functional Reach Test (FRT):

The patient will enter a standing position on a line marked on the floor. An inch tape will be attached to a wall at approximately shoulder height of the subject. The therapist will stand 5–10 feet away from the patient and instruct them to stand close to the wall without touching it, while facing the inch tape, with the shoulder flexed at 90° and the hand in a fist, figure (4). The therapist will record the starting position at the knuckle of the third metacarpal head on the ruler. The patient will then be instructed to reach as far forward as possible along the length of the tape without moving their feet. The therapist will once again record the location of the knuckle of the third metacarpal. Patients will be required not to lean against the wall during the test. If they lose balance, the therapist will stop the test. The scores will be determined by assessing the difference between the starting and ending positions. Three trials will be conducted with one minute of rest between each trial, and the average distance will be recorded in centimeters (**Alahmari et al., 2021**).

[figure not shown]

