- **Step-up and step-down**

Patients will perform forward, backward and lateral step-ups and step-downs using a 5cm – high sturdy wooden box. They will be instructed to keep their trunk upright. Patients will perform 10 repetitions of each component of the exercise.

[figure not shown]

Figure (5): Shows closed kinetic exercises adapted from (Ng et al., 2022).

3.2.b- Weight shifting exercises (WS):

The training will be conducted on both a stable surface and an unstable surface (balance board) and will consist of the following five tasks, figure (6):

1. In a standing position, shift the weight left and right maximally.
2. In a standing position, shift the weight forward and backward maximally.
3. In a standing position, perform bending and stretching of both knees.
4. In a standing position, raise and lower both feet's heels.
5. While sitting on a chair, perform sit-to-stand exercises on the balance board.

Each session will last for 30 minutes, occurring three days a week for a duration of 8 weeks (Lee et al., 2015).

Figure (6): Shows Weight Shifting adapted from (Diebal et al., 2011)

3.3. Complex decongestive therapy:

Complex decongestive therapy (CDT) for the treatment of lymphedema for both groups. CDT includes (skin care, manual lymphatic drainage, compression bandage and exercises).

4-Statistical procedures:

The collected data will be statistically analyzed using:

- Descriptive statistics (mean and standard deviations).
- Inferential statistics; ANOVA will be used to compare between subjects characteristics of the three groups.
- Shapiro-Wilk test will be used for testing normality of data distribution.
- Mixed MANOVA will be used to compare parametric measured variables between and within groups.
- Statistical analysis will be conducted using SPSS for Windows, version 20 (SPSS, Inc., Chicago, IL). Statistical significance will be set at the ($p < 0.05$).

REFERENCES

2. Ahmed, Y. F., Shafeek, M. M., & El-Kasem, S. T. A. (2021). Effect of cold versus heat modalities on dynamic balance in healthy adolescents. *Physiotherapy Quarterly*, 29(2), 56-61.

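### The stated 95% power belongs to an anteroposterior stability index that the trial does not collect, and is not shown for any of the three outcomes it does collect

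*Protocol*

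**What the plan says.** In the Protocol, Chapter III, section 1 (Subjects), the paragraph on sample size states: "Sample size calculation was done using Anteroposterior stability index". The value is taken from a cited earlier study of exercise for postural stability in post-mastectomy lymphedema. The settings are 95% power, alpha 0.05 and "number of measurements 2, for 4 groups and effect size = 0.6 using F-test MANOVA repeated measures within and between interaction". The result is a minimum of 52, to which 8 are added for dropout, giving 60 (15 per group).

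The measurement sections (2.1 in the Delimitations, and 2.1 and 3.1 in Chapter III) list three tools:

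- a smartphone app, described as a "smartphone-based machine learning algorithm for assessing standing balance";
- Timed Up and Go: "The time taken to complete this task will be measured in seconds using a stopwatch";
- functional reach, mean of three trials: "the average distance will be recorded in centimeters".

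Patients are assessed twice, before and after eight weeks. Section 4 (Statistical procedures) states: "Mixed MANOVA will be used to compare parametric measured variables between and within groups".

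**The concern.** The power statement is attached to a variable that will not be in the data set. The protocol gives no effect size or standard deviation for the app score, Timed Up and Go or functional reach, and does not argue that 0.6 applies to any of them. It also does not say which of the three the 95% is meant to describe.

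What is at stake is how a null result is read. The hypothesis is stated as no effect, so a non-significant finding could be taken as support for it from a trial with 95% power. If the true effect on a collected outcome were f = 0.4, a single-outcome test would miss it 37% of the time with 52 completers (1 − 0.634 = 0.366) and 29% with 60 (1 − 0.709 = 0.291), not 5%.

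**Working it through.** **1. Inputs from the protocol.** Groups k = 4, measurements m = 2, effect size 0.6, alpha 0.05, power 95%, stated N = 52 before dropout and 60 after.

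**2. Reproducing the stated figure.** For the within-between interaction in the multivariate repeated-measures test:

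- numerator df = (k − 1)(m − 1) = 3 × 1 = 3
- denominator df = N − k = 52 − 4 = 48
- noncentrality λ = f² × N = 0.36 × 52 = 18.72
- power from the noncentral F distribution = 0.951

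Fifty-two is the smallest N that reaches 0.95. At N = 60, λ = 0.36 × 60 = 21.6 and power is 0.976. The dropout step also matches: 52 × 1.15 = 59.8, rounded to 60.

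Other readings of the 0.6 do not give 52. Taking λ = f² × denominator df gives 56. The univariate repeated-measures formula gives 32 (correlation 0) or 20 (correlation 0.5). The first reading is therefore the one used.

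**3. What that figure covers.** The two measurements are used up by the two assessment times, so the calculation describes one outcome, tested on its change scores with 3 numerator df. A joint group-by-time test on three outcomes has 3 × 3 = 9 numerator df.

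**4. One collected outcome, other effect sizes.** Every f except 0.6 is an assumption.

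| f | λ at N = 52 | Power, N = 52 | λ at N = 60 | Power, N = 60 |
|---|---|---|---|---|
| 0.3 | 4.68 | 0.385 | 5.40 | 0.444 |
| 0.4 | 8.32 | 0.634 | 9.60 | 0.709 |
| 0.5 | 13.00 | 0.840 | 15.00 | 0.896 |
| 0.6 | 18.72 | 0.951 | 21.60 | 0.976 |

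The smallest f giving 95% power is 0.599 with 52 and 0.554 with 60. For 80% power it is 0.477 and 0.441.

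**5. Joint test on three outcomes.** Pillai's trace on the three change scores was simulated with 6,000 trials per case. Assumptions: arm means in the pattern 1, 1, 2, 0 (the two single exercises, combined, control) and an equal correlation r between the changes in each pair of outcomes.

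| r | f = 0.6 on one outcome, N = 52 / 60 | f = 0.6 on all three, N = 52 / 60 |
|---|---|---|
| 0 | 0.79 / 0.87 | >0.99 / >0.99 |
| 0.3 | 0.86 / 0.92 | 0.98 / 0.99 |
| 0.5 | 0.94 / 0.97 | 0.94 / 0.98 |
| 0.6 | 0.98 / 0.99 | 0.91 / 0.96 |
| 0.7 | >0.99 / >0.99 | 0.89 / 0.94 |

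Even if 0.6 is kept, joint power falls on either side of 95%. It depends on how many outcomes respond and how their changes correlate, and the protocol states neither.

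**6. Exercise arm against control, as an illustration.** By the noncentral t with pooled df 4n − 4, two-sided 0.05 and no multiplicity adjustment, the difference detectable with 80% power is about 1.12 SD of change with 13 per arm (df 48) and 1.04 SD with 15 (df 56).

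**The case against.** Borrowing an effect size from the nearest published study is ordinary practice, and here the source concerns the same population and construct. For the app there is a partial bridge: section 2.1.a of Chapter III cites agreement between smartphone and force-plate sway, including a correlation of 0.63. The test family also matches, since the sizing uses the interaction and a mixed MANOVA contains a group-by-time test. The stated N is correct, and nothing shows that the trial is underpowered. The lower power values come from assumed effect sizes and would apply to any trial that was too optimistic.

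Much of this stands. No number in the sample-size paragraph is wrong, and the tables above are sensitivity illustrations, not bounds. With f = 0.6 on all three outcomes and r = 0.9, for example, joint power is about 0.81 with 52, outside the range of correlations tabulated. The software output is a figure that is not shown, so the meaning of 0.6 is inferred from the exact reproduction.

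It does not remove the point. Agreement between devices does not establish an equal standardised treatment effect, the app section gives no effect-size value, and Timed Up and Go and functional reach have no bridge at all. Nor is this a detail left to a later analysis plan: the protocol itself fixes the basis of its power, on a measure outside its own list.

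**Conclusion.** The concern holds. The sample size is computed correctly for a single-outcome group-by-time test at f = 0.6, but the outcome behind that figure is not collected. The 95% is therefore unsupported for the app score, Timed Up and Go and functional reach, and the true power may be lower or higher.

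How far it could differ depends on values that the protocol does not give. For one outcome, power runs from 0.39 to 0.95 with 52 completers, and from 0.44 to 0.98 with 60, as f goes from 0.3 to 0.6. For the joint test with f = 0.6 on one or all three outcomes and r between 0 and 0.7, it runs from about 0.79 to above 0.99 with 52, and from 0.87 to above 0.99 with 60. This should be fixed, but it is no reason to change the number of patients.

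**What to change.** Keep N = 60 and make two changes.

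1. Before outcome data are seen, name one of the three collected outcomes as primary and its group-by-time interaction as the primary test.
2. Reword the sample-size paragraph along these lines:

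> The effect size f = 0.6 is an assumption borrowed from the anteroposterior stability index in a cited study, a measure not collected here. The 95% power (52 completers; 98% with 60) applies only to the four-group, single-outcome group-by-time test under that assumption. If f is 0.5, 0.4 or 0.3, power is 84%, 63% or 39% with 52 completers and 90%, 71% or 44% with 60.

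Optionally, add as an illustration the unadjusted difference between an exercise arm and control that is detectable with 80% power: about 1.12 SD of change with 13 per arm and 1.04 SD with 15.

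The cost is one reworded paragraph and one named outcome, with no added patients or visits. The 95% claim becomes conditional on an assumed effect size.

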This group will include 15 patients who will receive closed kinetic chain and Weight shifting exercises, in addition to complex decongestive therapy (CDT) for the treatment of lymphedema. The total exercise time will be 60 minutes; 30 minutes of

CKC and 30 minutes of WS exercise three times per week for eight weeks.

1.1.d- Group D (n= 15) (control group):

This group will include 15 patients who will receive complex decongestive therapy (CDT) for the treatment of lymphedema. CDT includes (skin care, manual lymphatic drainage, compression bandages, compression garments and exercises).

1.2 Criteria for the patient selection:

1.2. a. Inclusion Criteria:

- Women who had a history of BCRS with upper limb lymphedema.
- Age range of 40-60 years.
- The body mass index (BMI) is less than 30 Kg/m².
- Consciousness and ability to communicate orally or in writing.
- Treatment by unilateral mastectomy with lymph node dissection.
- No obvious abnormal spine morphology or postural abnormalities visible to the naked eye.
- All participants had moderate lymphedema according to the lymphedema severity assessment.

1.2.b. Exclusion Criteria:

The potential patients will be excluded if they meet one of the following criteria:

- Patients with metastases.
- Differences between lower limb length.
- Having acute or chronic vestibular, neurological, and orthopedic diseases.
- Surgery related to spine causing limitation of motion.
- Women with psychiatric disorders, reconstructive surgery.
- Bilateral mastectomy.

- Diagnosis with a neurological, skeletal, or rheumatic disorder or other disease that seriously affects body posture.
- History of bodily injury such as a spinal, shoulder, or neck injury, resulting in permanent alteration of the normal body posture prior to the unilateral mastectomy.
- Failure to complete follow-up for any reason over the course of the study.
- Peripheral polyneuropathy, cognitive dysfunction.
- Patients taking medication that affects body balance.
- Severe arthritis or orthopedic conditions in their lower extremity
- Poor conditioning, acute pain in any reason,
- Neurological disorders including visual problems.

2-Equipment:

2.1- Measurement equipment:

2.1.a. Kinesis Balance™ fall prevention app:

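### Failure to complete follow-up is listed as an exclusion criterion, although it can apply only to patients who are already randomised

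*Protocol*

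**What the plan says.** All references are to Chapter III of the protocol unless stated otherwise.

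- **1.2.b Exclusion Criteria.** The list opens with "The potential patients will be excluded if they meet one of the following criteria", and one of its bullets is "Failure to complete follow-up for any reason over the course of the study".
- **3.1 Measurement procedures.** Assessment takes place twice: "All patients will be evaluated before and after eight weeks of using closed kinetic chain and weight shifting exercises". No other post-baseline visit is described.
- **1 Subjects and 1.1 Design.** Allocation is by chance: "The patients will be subdivided randomly into four equal groups by using simple randomization technique 1:1 ratio". The design is described as "The study will be four-armed, single-blind (assessor), parallel-group, randomized control trial".
- **1 Subjects, sample size calculation.** Losses are allowed for: "adding 8 subjects (15%) as drop out, so total sample size is 60 subjects". The calculation is for the "F-test MANOVA repeated measures within and between interaction".
- **4 Statistical procedures.** "Mixed MANOVA will be used to compare parametric measured variables between and within groups". The section says nothing that would override the exclusion bullet.
- **Basic Assumptions (in the introductory part).** It is assumed that no patient leaves the study.

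**The concern.** An eligibility criterion has to be decidable before allocation. This one depends on what happens up to week 8. Taken at its word, it tells the investigator that a randomised patient who misses the week-8 assessment, whatever her reason, is an excluded patient.

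Two things are at stake:

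1. **Selection after randomisation.** The groups compared would no longer be the groups that were randomised. If loss differs by arm and is related to balance, which is the outcome, the comparison is biased. Unequal loss is plausible though not shown: the added exercise is nil in group D, 30 minutes per session in A and B, and 60 minutes in C, three times a week for eight weeks.
2. **No incentive to collect the data.** Once a missing week-8 test is a ground for exclusion, nobody has a reason to bring the patient back for it.

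**Working it through.** **Step 1: when can the criterion be met?** Section 3.1 gives two assessments, before and after eight weeks. Failure to complete can be known only after the first and by the time of the second. Patients followed over that period have been randomised (section 1). The bullet therefore cannot act at screening.

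**Step 2: the plan's own figures.** Inputs from the sample size section: 4 groups, 2 measurements, effect size 0.6, alpha 0.05, power 95%. For the interaction test, df1 = (4-1)(2-1) = 3, df2 = N-4, noncentrality = N x 0.6^2.

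- N = 51: power 0.946. N = 52: power 0.951. The stated minimum of 52 is reproduced.
- 52 x 1.15 = 59.8, hence 60, as stated.
- At the planned loss, 8/60 = 13.3% of randomised patients would meet the criterion. The 52 left have the planned power, so power is not the issue; selection is.

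**Step 3: illustration of possible bias.** The total of 8 losses comes from the protocol. Everything else is assumed: how the losses split over A/B/C/D; a pre-post correlation r of 0.5-0.7; and a correlation rho between the tendency to drop out and a poor week-8 value. The simulation has 15 per arm, normal values with SD 1, no true effect and 40,000 runs per scenario. The result is the bias in C minus D for completers' change from baseline, in SD units.

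| Split A/B/C/D | rho 0.5 | rho 1 |
|---|---|---|
| 2/2/2/2 | about 0 | about 0 |
| 1/2/4/1 | 0.04-0.08 | 0.09-0.15 |
| 1/1/5/1 (extreme) | 0.06-0.10 | 0.12-0.19 |

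For the milder split 1/2/3/2 the bias is 0.01-0.05 over rho 0.25 to 1.

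Hand check of the extreme row: at rho 1 the unadjusted week-8 means of C and D differ by 0.39. The change contrast carries a fraction (1-r) of that: 0.39 x 0.5 = 0.195 and 0.39 x 0.3 = 0.117. At rho 0.5 these halve to about 0.10 and 0.06.

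**Step 4: scale and sign.**

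- Standard error of the contrast with 13 per arm: sqrt(2(1-r)) x sqrt(2/13) = 0.39 (r = 0.5) or 0.30 (r = 0.7). The extreme case is therefore at most about half a standard error (0.19/0.39).
- If 8 of 60 were lost purely at random, C and D losses would differ by 4 or more in 5.8% of cases.
- With split 1/1/1/5, or with 1/1/5/1 and dropout tied to a poor baseline, the same sizes appear with the opposite sign.

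**Step 5: what the remedies do (split 1/1/5/1).**

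- *Delete the bullet only.* A mixed MANOVA with two measurements still uses complete pairs, so the analysed patients are the same.
- *Obtain the week-8 test from half of those who would be lost.* The bias falls to 0.02-0.04 (rho 0.5) and 0.05-0.08 (rho 1).
- *Likelihood-based mixed model on what remains missing.* The bias is about 0 if dropout depends on baseline. If it depends on the week-8 value, 0.10-0.15 (rho 0.5) and 0.23-0.31 (rho 1) remain, which is more than the completers' change contrast. The model leaves roughly a fraction (1-r^2) of the shift, against (1-r) for the change contrast.

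**The case against.** **The list is for screening.** The bullet stands under patient selection and the lead-in speaks of potential patients, so it may be a withdrawal definition that strayed into the wrong list. That may well be its origin. It does not rescue the text: the bullet names an event that cannot occur before allocation, and a withdrawal rule would still remove randomised patients.

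**The bullet changes nothing in the analysis.** A reader might infer that the bullet by itself turns the trial into a completers-only comparison. The documents do not support that. The planned mixed MANOVA would lose patients without a week-8 value in any case. This objection stands and limits the point: the bullet endorses the exclusion and removes the reason to prevent the gap, but it is not the sole cause. Nor does the protocol say in its statistical section that these patients leave the analysis; that follows from the exclusion list.

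**It reaches further than the week-8 test.** One might also read follow-up as covering the exercise sessions, so that a patient who stopped exercising but came for the test would be excluded too. The protocol does not define the term, and the only follow-up assessment it describes is the one at eight weeks, so that reading is not relied on here.

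**Analysis sets and missing data belong in the statistical analysis plan.** Correct, and no such omission is raised. The finding concerns a rule that the protocol states. An analysis plan that kept all randomised patients would contradict it.

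**The numbers are assumed and small.** Also correct. The milder splits give about 0 to 0.05 SD, and the larger values need a marked imbalance in loss.

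**Conclusion.** The criterion is wrong as stated: it is an exclusion rule that can act only after randomisation, and nothing in the protocol overrides it. It sanctions dropping randomised non-completers and discourages collecting their week-8 data. This is worth correcting, but it does not show that the results will be materially biased.

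Size and direction cannot be derived from the documents. Under assumed splits of the 8 planned losses, an assumed pre-post correlation of 0.5-0.7 and an assumed link between dropout and outcome, the bias runs from about 0 with equal loss to 0.1-0.2 SD with an extreme split, and the sign can go either way. A reader might infer a known bias in favour of the exercise arms, or a loss of planned power; neither follows. The conclusion that the bullet is misplaced rests on the wording and the assessment schedule alone and needs none of these assumptions.

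**What to change.** 1. Delete the bullet from section 1.2.b.
2. Treat non-completion as loss to follow-up, and report it by arm with reasons.
3. State that all randomised patients stay in their allocated arm, and that the week-8 tests already planned are sought from every one of them whatever their exercise attendance. This step carries the protection, because deletion alone leaves the mixed MANOVA as it is.
4. Optionally, add a likelihood-based mixed model or multiple imputation as a sensitivity analysis only. State that it relies on data being missing at random, and that it can be more biased than the completers' change contrast when dropout depends on the week-8 value. The choice of model can be left to the statistical analysis plan.

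Cost: one bullet removed, two or three sentences added, and some effort to recall patients who stop, about 8 at the planned loss, for one assessment. No extra patients and no new procedures are needed.

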Figure (4): Shows Measurement of dynamic balance by functional reach test. **a** Starting position. **b** Final position adapted from (**Alahmari et al., 2021**)

3.2-Therapeutic procedures:

3.2.a- Closed kinetic chain exercises (CKC):

Three sets of ten repetitions will be performed in each exercise session and a duration of 30 minutes will be conducted three times a week for eight weeks. There will be two-minute breaks between sets to avoid fatigue (**Sajjad et al., 2024**).

All types of CKC exercises can be performed with or without weights. (**Thabet et al., 2017**).

The following closed kinetic chain exercises will be carried out by the patients in the treatment group figure (5) (**Gbiri et al., 2013; Adegoke et al., 2019**):

- Quadriceps Setting Exercise**

Patients will sit on a chair with their back supported, knee extended and heel on the floor. They pressed their heels against the floor and thighs against the seat of the chair. The position was held for a count of 10 after which the participant relaxed.

- Toe Raises**

Patients will be standing with feet approximately shoulder width apart and extend arms out slightly forward and lower than the shoulder. Lift both heels of the floor and try to hold the position for 10 seconds.

- Standing with feet side by side**, hold arms in the same position as described in the previous exercise. Place one foot on the inside of the opposing ankle and try to hold the position for 10 seconds.
- Standing on one extremity** for 30 seconds (repeated in both extremities), leaning forward, backward, and to the sides on one extremity (eyes open), leaning forward, backward, and to the sides on one extremity (eyes closed), and sitting down and standing up from a highchair slowly.

- **Wall Squat**

With feet shoulder-width apart, knees aligned over ankles and back to wall, tighten buttocks and quads, attempting to tighten VMO first, then slide down wall until knees are bent, Hold.

- **Double Leg Squat**

Stand with feet shoulder-width apart, using hand support as necessary. Align knees over ankles, tighten buttocks, tighten quads, attempting to tighten VMO first. Bend knees. Do not allow knees to go forward past toes. Keep your back straight, bending forward at the hips. Hold for 5 to 10 seconds. Return to standing.

- **Lunge**

From standing position (hand support as needed), keep the forward knee over the ankle while allowing the “back” knee to bend, lunge forward. Return. Alternate legs.

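### Does the closed kinetic chain session contradict its own 30-minute length?

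*Protocol*

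**What the plan says.** Chapter III, 3.2.a of the protocol sets the CKC session in one sentence, which also fixes three sessions weekly over eight weeks: "Three sets of ten repetitions will be performed in each exercise session and a duration of 30 minutes will be conducted". It adds "There will be two-minute breaks between sets to avoid fatigue" and then "The following closed kinetic chain exercises will be carried out by the patients in the treatment group".

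Eight items follow, and several carry a dose of their own:

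- Quadriceps setting: "The position was held for a count of 10 after which the participant relaxed".
- Toe raises: "Lift both heels of the floor and try to hold the position for 10 seconds".
- Foot-at-ankle stand: a 10-second hold.
- One-leg stance: "for 30 seconds (repeated in both extremities"), followed by leaning and slow sit-to-stand.
- Wall squat: a hold of unstated length.
- Double leg squat: "Hold for 5 to 10 seconds".
- Lunge: no hold.
- Steps: "Patients will perform forward, backward and lateral step-ups and step-downs", with ten repetitions per component.

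The group descriptions (Chapter III, 1.1.a to 1.1.c) give 30 minutes of exercise for Group A, 30 for Group B, and 30 + 30 for Group C. Weight shifting (3.2.b) is set by time only, also 30 minutes.

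**The concern.** The session has a set count, a break length, a list of exercises, a separate step rule and a clock time, and the text does not rank them. The two most natural readings of the set rule each break something else that the protocol states. If no reading worked, the CKC content of Groups A and C (30 of 60 patients) would be undefined. The time match between Groups A and B, and the equal halves of Group C's hour, would also be in doubt. Patients come from two sites, so staff might deliver different sessions from the same text. The comparisons of A and C with the control group would still be randomised, but the treatment behind them could not be repeated from the protocol.

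**Working it through.** **Inputs** (Chapter III, 3.2.a): 3 sets of 10; 2 minutes between sets; 8 listed exercises; holds of 10 s for three exercises, 5 to 10 s for the double leg squat and 30 s per leg for the one-leg stance; steps in 3 directions x 10; stated length 30 minutes.

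**Assumptions:** a count of 10 takes 10 s, and a movement without a hold takes 2 to 4 s. Leaning, the untimed wall-squat hold and change-over are not counted.

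**Sets as a session total.**
- Repetitions: 3 x 10 = 30. Steps need 3 x 10 = 30, which leaves 0 for the other seven exercises.
- If exercises rotate between sessions instead: 30 x 10 s + 2 x 2 min = 9 min, well short of 30.

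**Three sets for each of the eight exercises, breaks inside the 30 minutes.**
- Breaks within exercises: 8 x 2 x 2 min = 32 min. With a break between all 24 sets: 23 x 2 = 46 min.
- Holds without the one-leg stance: 3 x 30 x 10 s = 15 min, plus 30 x (5 to 10 s) = 2.5 to 5 min, together 17.5 to 20 min.
- Total at least 32 + 17.5 = 49.5 min. This does not fit.

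**Three rounds of all exercises.**
- Breaks: 2 x 2 = 4 min.
- One-leg stance at its own stated dose, once per leg per round: 3 x 2 x 30 s = 3 min.
- Breaks plus holds: 4 + 17.5 + 3 = 24.5 min to 4 + 20 + 3 = 27 min.
- Remaining movements: 30 each of wall squats, lunges and steps (90), or 120 with sit-to-stands. At 2 s these take 3 to 4 min, at 4 s 6 to 8 min.
- Total: 24.5 + 3 = 27.5 min to 27 + 8 = 35 min, a range that includes 30.
- If the one-leg stance also had to be done ten times per round (15 to 30 min), the total would be at least 4 + 17.5 + 15 = 36.5 min. If the foot-at-ankle stand is done on both sides at each repetition, 5 min are added.

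**Three sets per exercise, breaks outside the 30 minutes.**
- Holds 17.5 to 20 min, one-leg stance 3 min, movements 3 to 8 min: 23.5 to 31 min.

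**A subset per session, for example three exercises.**
- 9 sets need 8 breaks: 8 x 2 = 16 min. This leaves 14 min = 840 s for 90 repetitions, about 9.3 s each. This fits.

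| Reading | Minutes | Against 30 |
|---|---|---|
| Session total, rotating exercises | 9 | too short |
| Each exercise, breaks inside | at least 49.5 | too long |
| Three rounds, stance at own dose | 27.5 to 35 | can fit |
| Each exercise, breaks outside | 23.5 to 31 | can fit |
| Three exercises per session | 30 at 9.3 s per repetition | can fit |

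**The case for a change.** The strongest case for a change is that each fitting reading needs something the protocol does not state. Three rounds fit only if the one-leg stance is exempt from the ten-repetition rule and the pace is brisk: 3 to 5.5 minutes remain for 90 to 120 movements, or 1.5 to 3.7 s each, with nothing left for leaning or change-over. Placing breaks outside the 30 minutes would lengthen the visit to about an hour if there are 32 minutes of breaks. A subset sits awkwardly with a sentence that says the listed exercises will be done. Across readings the repetitions run from 30 to 240 or 300 per session, and an SAP would not settle an exercise dose.

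Part of this stands. The wording is loose, and the protocol does not say what a set belongs to. But the one-leg stance and the steps carry doses of their own, and letting an item's own dose override a general rule is an ordinary way to read such a list. The group descriptions speak of exercise time, which need not include rest. Nothing says that all eight exercises are done in every session.

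The eight- to tenfold spread in repetitions joins two readings that both fail: one leaves nothing for seven exercises, the other needs at least 49.5 minutes. It does not estimate what would be delivered. The two sites are named as places from which patients are selected, and the protocol does not say that different staff deliver CKC at each.

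**Conclusion.** The concern does not hold as a contradiction. The protocol leaves open what the sets and breaks apply to and whether breaks count in the 30 minutes. Two readings then fail (32 minutes of breaks alone, or no repetitions left for seven exercises), but at least three others can be delivered in about 30 minutes. That result rests on the assumed 2 to 4 s per movement, on the one-leg stance being done at its own stated dose where it is counted, and on leaving out leaning and the untimed wall-squat hold.

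The gap is one that treating staff can fill in practice. The session length is given as 30 minutes in 3.2.a and in the descriptions of Groups A and C, with the same frequency and number of weeks, so the clock gives them a common frame. The exercises and most holds are named. The weight-shifting arm is described by time alone and works on the same basis.

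Nothing statistical depends on the answer: allocation, the 60 patients, the outcome measures and the planned comparisons are the same under every reading. If 3.2.a is edited for another reason, its set, break, list and duration wording should be reconciled with 1.1.a and 1.1.c. Which reading is intended is for the sponsor to say, and none is preferred here.
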